A total of 60 bipolar and healthy comparison subjects (n=30 per group, 21-26 years of age, 50% women, with no history of a severe AUD) will be recruited from the greater Austin area. We included individuals with a history of mild/moderate AUDs as doing so is more generalizable since it is common that individuals in this age group experiment with alcohol use. We will exclude individuals with a history of symptoms suggesting dependence (which is what you see in individuals with severe AUDs). Subjects will be recruited through multiple venues to optimize subject enrollment. Once recruited and enrolled, subjects will undergo detailed structured clinical evaluations to verify inclusion and exclusion criteria followed by structural MRI assessments. Following standard beverage administration procedures, they will then complete measures of subjective response to alcohol and fMRI scans while under the influence of alcohol or a placebo condition (counter-balanced). All subjects will be euthymic and alcohol/placebo sessions will occur within 3 days of each other. fMRI assessments will include a continuous performance task with emotional and neutral distractors (CPT-END) and resting state scans. Participants will first complete the CPT-END task at baseline (outside the scanner) before their alcohol or placebo session. Our recent data suggest differences in ventral brain networks when viewing emotional stimuli for the first time compared to the second time (associated with habituation of emotional networks), but that there are minimal differences between the second and third viewings. We will investigate (Aim 1) differences in subjective response to alcohol between bipolar and healthy participants and associations with recent drinking patterns and (Aim 2) differences between bipolar and healthy young adults in alcohol-induced changes, compared to placebo, in regional activation in vPFC emotional networks and connectivity among these regions.

4 Data Analysis

Describe the data analysis plan, including any statistical procedures or power analysis.

To input text, click in the light grey area below.

Aim 1: Between Group Differences in Subjective Response to Alcohol

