Group (bipolar, healthy)-by-condition (alcohol, placebo)-by-time of subjective response interactions on subjective response to alcohol will be modeled, covarying beverage condition order, biological sex, and age with SEAS and DEQ subscale scores as the dependent variables. Time of subjective response (pre- and post-scan) and beverage condition (alcohol, placebo) will be within-subject factors and group an independent between-subject factor. Following no group-by-condition-by-time of subjective response interaction, the three-way interaction term will be dropped and group-by-condition interactions investigated. Following no two-way interaction, the two-way interaction term will be dropped and main effects of group and condition assessed. Findings for these planned analyses will be considered significant at $p < 0.05$.

Between Group Differences in Functional Connectivity to Alcohol

Using the CONN Toolbox, we will perform region of interest (ROI)-to-ROI bivariate correlation first-level analysis to calculate fisher transformed correlation coefficients (measure of functional connectivity (FC)) between a priori ROI-to-ROI connections during placebo and alcohol condition CPT-END fMRI sessions. We will extract Fisher transformed correlation coefficients between ROI-to-ROI connections during emotional stimuli and during squares for analysis. We will calculate the contrast: FC during emotional stimuli minus FC during squares for alcohol and placebo conditions, in line with prior studies. A priori ROIs will be defined using the FSL Harvard Oxford Atlas in the CONN toolbox, and included bilateral insula, amygdala, nucleus accumbens (NAcc), ventromedial PFC (vmPFC), lateral orbitofrontal cortex (OFC), subcallosal cortex (SCC), and inferior frontal gyrus pars triangularis (IFG.tri). We will examine ROI-to-ROI connections between limbic/subcortical regions (insula, amygdala, or NAcc) with ventromedial PFC (vmPFC or SCC) and ventrolateral PFC (OFC or IFG.tri) regions.

We will use a mixed model to examine group by condition by hemisphere (left, right) interactions on ROI-to-ROI FC response to emotional stimuli (contrast: emotional stimuli - squares). Group will be an independent between-subject factor, condition and hemisphere within-subject factors, and ROI-to-ROI FC the dependent variable. Results of primary models will be considered significant at $p \leq 0.004$ (Bonferroni correction for twelve ROI-to-ROI connections).

STUDY PROCEDURE DESCRIPTION

5

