60 total participants will complete baseline assessment, alcohol and placebo sessions (30 diagnosed with bipolar disorder and 30 healthy comparison subjects). All subjects will be between 21 and 26 years of age. We plan to include equal numbers of males and females and minorities in proportions representative of the population in the greater Austin area. We expect many subjects will be students at University of Texas. We also expect to recruit approximately 10 participants who will not meet inclusion/exclusion criteria following initial clinical assessment (e.g., they do not meet criteria for bipolar disorder type I). These individuals will be compensated for completing the clinical interview but will not be invited to come in for the baseline scan or the alcohol/placebo MRI session. Total participants to be recruited includes 70 young adults.

b Minimum Age

To input text, click in the light grey area below.

21 years of age

c Maximum Age

To input text, click in the light grey area below.

26 years of age

d Inclusion Criteria

To input text, click in the light grey area below.

Eligibility will be determined by the staff consenting subjects, under the supervision of the Principal Investigator.

Inclusion Criteria:

All Subjects:

1. ages 21-26 years
2. male and female subjects from all racial and minority groups

Subjects with Bipolar Disorder:

1. diagnosis of bipolar disorder type I

7

Total Sample Size

To input text, click in the light grey area below.

Total study participants that will be recruited are 70 young adults (30 participants with bipolar disorder and 30 typically developing comparison young adults will complete the study and estimate 10 participants will not meet inclusion/exclusion criteria following initial clinical interview).

8

Sample size rationale

To input text, click in the light grey area below.

The proposed N in this study has the power to detect medium to large effects. At an alpha=0.05, 30 subjects per group will provide >80% statistical power to detect a within subject ES $d \geq 0.5$ and a between group ES $d \geq 0.7$. This compares favorably with large ESs calculated from between group differences in subjective response to alcohol in youth at risk for bipolar disorder (defined by previous hypomanic experiences; $d > 1.3$) [53]. Our design

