is sufficiently powered for both aims. In preliminary data, we observed large between group ESs when comparing differences in subjective response to alcohol (with Cohen's d ranging from 0.7 to 1.3; Aim 1a), large within group ESs when performing correlations between response to alcohol and drinking patterns (r 's ranging 0.7 to 0.9, Aim 1b), and large ESs in healthy participants (when comparing alcohol scan to baseline scan for Aim 2) with Cohen's d ranging from 0.4 to 3.3. Conversely, we observed small ESs in bipolar disorder when comparing alcohol and baseline scans (with ESs as low as 0.03). Calculated sample size required to reach significance from pilot data ranged between $N=3$ to $N=29$ across both aims. The recruitment of 30 per group through this application ensures adequate power for testing our hypothesis.

OBTAINING INFORMED CONSENT

9

Consent and Assent Processes

Provide a detailed description of the consent process including who will obtain consent, where, and when consent will occur in such a manner that participants have sufficient time for adequate consideration.

To input text, click in the light grey area below.

Subjects are consented on a 1:1 basis with the PI, co-investigators, or research associates. The staff member reads the consent form aloud with the subject. The subject is encouraged to stop the staff member and ask questions along the way. In addition, the staff member anticipates questions and describes anything that seems unclear in more detail. After reading the consent form, the subject is asked again if they have any questions. Any questions are answered. They are then asked by the staff member whether he/she wishes to participate (consent). This enhances independent decision-making by never assuming the subject automatically wants to participate after reading the consent form.

Subjects will be asked if they will permit us to stay in contact with them in order to invite them to return for the second assessment and scanning session 1-year later. There may be some subjects who may only be willing to participate in the imaging component but will not wish to give a saliva sample and choose not to participate in the genetic component. In that case they will only be consented for the interview and the imaging component of the study.

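### Section 8 computes power only at alpha 0.05 and claims adequacy for both aims, but the connectivity models are judged at p ≤ 0.004, where power at the stated between-group d = 0.7 is about 40% per connection two-sided (49% one-sided)

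*Combined protocol and SAP*

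**What the plan says.** Section 8 states: "At an alpha=0.05, 30 subjects per group will provide >80% statistical power to detect a within subject ES" of at least 0.5, and a between-group d of at least 0.7. No other alpha appears in the section, and it does not say whether the tests are one- or two-sided. It goes on to say that the design "is sufficiently powered for both aims" and that recruiting 30 per group "ensures adequate power for testing our hypothesis".

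Section 3 defines Aim 2 as bipolar-versus-healthy differences in alcohol-induced change, compared with placebo, in "regional activation in vPFC emotional networks and connectivity among these regions". The front matter lists functional connectivity among the primary outcomes.

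Section 4, under the functional connectivity heading, gives the model: "We will use a mixed model to examine group by condition by hemisphere (left, right) interactions on ROI-to-ROI FC response to emotional stimuli". Its primary results are significant at p ≤ 0.004, described as a "Bonferroni correction for twelve ROI-to-ROI connections". The Aim 1 subjective-response models use p < 0.05.

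The Aim 2 pilot evidence in section 8 is a range of d from 0.4 to 3.3 in healthy participants "when comparing alcohol scan to baseline scan for Aim 2". It continues: "Conversely, we observed small ESs in bipolar disorder when comparing alcohol and baseline scans", with values as low as 0.03. Section 8 also reports pilot-based sample sizes of 3 to 29 across both aims, without stating alpha or power.

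**The concern.** The power statement and the decision rule for a primary outcome use alphas that differ about twelvefold. Section 8 is the only support for the power claim, and because it covers both aims, a reader would naturally carry more than 80% power at d = 0.7 over to each FC connection. If power at the planned threshold is about half of that, a non-significant FC result says much less about the absence of a group difference than section 8 implies.

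**Working it through.** **Inputs.** From section 8: 30 completers per group, between-group d = 0.7, within-subject d = 0.5, alpha 0.05, stated power above 80%. From section 4: FC threshold 0.004, from 3 limbic/subcortical regions × 4 prefrontal regions = 12 connections and 0.05/12 = 0.00417. Sidedness is not stated, so both versions are shown.

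**Model.** With complete balanced data and no covariates, the group-by-condition term equals a two-sample t test on each person's hemisphere-averaged alcohol-minus-placebo FC difference. Here d is the group difference in that change divided by its SD. Power is the probability that a noncentral t variable exceeds the critical value.

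- Between groups: df = 2 × 30 − 2 = 58, noncentrality = d × √(30/2). At d = 0.7 this is 0.7 × 3.873 = 2.711.
- Within one group: df = 29, noncentrality = d × √30. At d = 0.5 this is 2.739.
- Within all 60 pooled: df = 59, noncentrality = 0.5 × √60 = 3.873.

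**Step 1: the plan's own figure, alpha 0.05**

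| Comparison | Two-sided | One-sided |
|---|---|---|
| Between, d = 0.7 (critical t 2.002 / 1.672) | 76.0% | 85.0% |
| Within, d = 0.5, n = 30 (critical t 2.045 / 1.699) | 75.4% | 84.8% |
| Detectable d at 80%, between | 0.74 | 0.65 |
| Detectable d at 80%, within, n = 30 | 0.53 | 0.46 |

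The stated >80% is reproduced for both effects only with one-sided tests. Two-sided, the within-subject claim holds only if all 60 participants are pooled (97%).

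**Step 2: between groups at the FC threshold, alpha 0.004, per connection**

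| d | Two-sided (critical t 2.998) | One-sided (critical t 2.747) |
|---|---|---|
| 0.7 | 39.6% | 49.1% |
| 0.8 | 54.4% | 63.8% |
| 0.9 | 68.5% | 76.7% |
| 1.0 | 80.4% | 86.5% |
| 1.3 | 97.6% | 98.7% |

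Using the unrounded 0.05/12 changes the first row little, to 40.1% and 49.7%. The detectable d at 80% power is 1.00 two-sided and 0.93 one-sided. For scale only, 80% power at d = 0.7 would take 59 per group two-sided or 52 one-sided.

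**Step 3: what per-connection power leaves out.** The chance of at least one significant connection is higher. It was simulated with 20,000 data sets per case, two-sided at 0.004, with true d = 0.7 in the affected connections. The between-connection correlations are assumptions, because the documents give none.

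| Affected connections | Correlation 0.3 | 0.5 | 0.7 |
|---|---|---|---|
| 3 | 70% | 65% | 58% |
| 12 | 94% | 87% | 77% |

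**The case against.** The strongest reply is that section 8 ties d = 0.7 explicitly to alpha 0.05 and never says FC was planned around it. A large effect in healthy participants beside a near-zero one in bipolar disorder is compatible with a between-group difference above 1.0, where FC power reaches 80%. That is possible, but the same pilot figures are compatible with much less. They compare alcohol with baseline rather than with placebo, and they are reported within each group. The documents give no effect size for the difference in change. The pilot-based range of 3 to 29 does not help either: with no alpha or power stated, it cannot show adequacy at 0.004.

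Second, the hypotheses in section 1 are directional, and one-sided tests reproduce both stated figures at alpha 0.05. This stands as a reason to ask for sidedness rather than presume it. It does not rescue the FC claim, since one-sided power at 0.004 is still only 49%.

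Third, the named FC test is the three-way term with hemisphere, whereas the 40% is for group-by-condition. The group-by-condition contrast is the one that matches hypothesis (b). With complete balanced data, the three-way term also reduces to a two-sample t test on a per-person contrast. Its power at d = 0.7 on its own scale is the same 40%. How large d would be on that scale cannot be derived from the documents.

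Fourth, not every FC contrast is short of power. A pooled alcohol-placebo contrast in all 60 participants at d = 0.5 has 80.5% power even at 0.004 two-sided. This is correct and limits the point to the between-group difference in change, which is what hypothesis (b) concerns.

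Finally, the stricter threshold does not threaten validity. That is also true; the fault is in the stated power, not in the test.

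**Conclusion.** The concern holds. Section 8 claims adequacy for both aims from a calculation at alpha 0.05 that does not apply to the FC models. At their threshold, a true between-group d of 0.7 in a given connection would miss significance about 60% of the time two-sided (51% one-sided). Thirty per group gives 80% power per connection only for d of about 1.00 (0.93). Part of the distance from the stated >80% comes from unstated sidedness: 76% rather than 85% at alpha 0.05 if tests are two-sided.

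These figures assume 30 completers per group, complete balanced data, no covariates, and d defined on the alcohol-minus-placebo change. They are per connection, not study-level. The point should be corrected because it concerns a primary outcome and affects how a null FC result is read.

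**What to change.** Restate section 8 by aim and state sidedness.

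- **Aim 1 (alpha 0.05).** If two-sided: about 76% power at between-group d = 0.7 and 75% at within-subject d = 0.5 in one group of 30, or detectable d of about 0.74 and 0.53. If one-sided tests are intended, say so and give 85% for each. Say whether the within-subject figure refers to one group of 30 or to all 60.
- **FC models (p ≤ 0.004).** If two-sided: 80% power per connection for a between-group d of about 1.0 in alcohol-minus-placebo FC change, and about 40% at d = 0.7. If one-sided: detectable d about 0.93, and 49% at d = 0.7. The pooled within-subject contrast at d = 0.5 (80.5% two-sided) can be reported alongside. State that the figures rest on a two-sample comparison of change scores.
- **Claims.** Remove the statement of sufficient power for both aims, and qualify the closing statement of adequate power, as they apply to FC.
- **Pilot evidence.** Note that the Aim 2 pilot effects are within-group alcohol-versus-baseline contrasts that do not directly support the group-by-condition test, and give the alpha and power behind the range of 3 to 29.

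The cost is wording in section 8 and a less favourable stated power. Sample size, analysis and conduct do not change.

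### Section 8 claims adequate power for Aim 2, but its only Aim 2 pilot effects are within-group, alcohol versus baseline scan; no effect size is given for the between-group, alcohol-versus-placebo contrast that Aim 2 tests

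*Combined protocol and SAP*

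**What the plan says.** Section 8 of the combined protocol and SAP starts from a general statement: "At an alpha=0.05, 30 subjects per group will provide >80% statistical power to detect a within subject ES" of at least 0.5, and a between-group effect of at least 0.7. It then says that the design has enough power for both aims and supports this with preliminary data. For Aim 2 these are effects seen "when comparing alcohol scan to baseline scan for Aim 2", with d from 0.4 to 3.3 in healthy participants, and effects as low as 0.03 for the same comparison in bipolar disorder. The sample size needed according to the pilot data is given as 3 to 29 over both aims, and 30 per group is said to be adequate.

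Section 3 (Design and Methodology) defines Aim 2 as "differences between bipolar and healthy young adults in alcohol-induced changes, compared to placebo". Section 4 (Data Analysis) tests connectivity in a mixed model with group, condition (alcohol, placebo) and hemisphere, at p ≤ 0.004 for twelve connections. Section 5 (Procedure Description) says that alcohol and placebo scans are compared within subject and the resulting changes compared between groups. It also says that the CPT-END task is not run in the scanner at baseline.

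**The concern.** The pilot effects differ from the Aim 2 estimand in two ways.

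- **Comparator.** They contrast alcohol with a baseline scan, not with placebo. Section 5 says that the placebo is there to model expectancy, which an alcohol-minus-baseline contrast leaves in. Because CPT-END is not scanned at baseline, this trial cannot form the pilot contrast for the task analysed in section 4.
- **Level.** They are changes within each group. Aim 2 asks whether the change differs between groups, and section 8 gives no between-group effect for it.

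What is at stake is the reading of the Aim 2 result. A protocol that asserts adequate power invites a non-significant connectivity result to be taken as informative about the absence of a group difference. If the assertion has no matching basis, the reader cannot tell how large a difference the trial could have missed.

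**Working it through.** **Inputs.** 30 per group (section 6a: "60 total participants will complete baseline assessment, alcohol and placebo sessions (30 diagnosed with bipolar disorder and 30 healthy comparison subjects"); alpha 0.05, within-subject d=0.5 and between-group d=0.7 (section 8); connectivity threshold 0.004, which is 0.05/12 = 0.00417 rounded (section 4); pilot effects 0.4 to 3.3 and 0.03 (section 8). The documents do not state whether tests are one- or two-sided.

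**Formula.** For a two-sample t-test with n per group, power = P(T > t_crit), where T is noncentral t with 2n−2 = 58 degrees of freedom and noncentrality d√(n/2) = d√15 = 3.873d. For the paired test, the degrees of freedom are 29 and the noncentrality is d√30.

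**Step 1: the plan's own figure.**

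| Test | Noncentrality | t_crit, one-sided 0.05 | Power | t_crit, two-sided 0.05 | Power |
|---|---|---|---|---|---|
| Between groups, d=0.7 | 2.711 | 1.672 | 85% | 2.002 | 76% |
| Within subject, d=0.5, n=30 | 2.739 | 1.699 | 85% | 2.045 | 75% |

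The stated figure of over 80% is reproduced for both with a one-sided test.

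**Step 2: pilot contrast against tested contrast.**

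| | Pilot effects in section 8 | Aim 2 in sections 3 to 5 |
|---|---|---|
| Comparator for alcohol | baseline scan | placebo scan |
| Level | within each group | difference between groups |
| Effect size given | 0.4 to 3.3; as low as 0.03 | none |

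The 3-to-29 range is said to come from pilot data and to cover both aims. The baseline-scan effects are the only Aim 2 pilot data reported, so the Aim 2 part of that range has no other visible source. Its derivation is not stated.

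**Step 3: can the pilot effects be converted?** Only by assumption. If the standard deviations of change were equal in the two groups, and baseline could stand in for placebo, subtracting 0.03 from each end of the healthy range gives between-group values of 0.4 − 0.03 = 0.37 and 3.3 − 0.03 = 3.27. With 30 per group, d=0.37 has 29% power at two-sided 0.05 and 7% at 0.004. At d=3.27 power is essentially 100%. The pilot data therefore do not settle Aim 2 power in either direction.

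**Step 4: what 30 per group can detect.** The group difference in alcohol-minus-placebo change is treated as a two-sample comparison, two-sided, with 58 degrees of freedom.

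| Between-group d | Power at 0.05 | Power at 0.004 |
|---|---|---|
| 0.4 | 33% | 8% |
| 0.5 | 48% | 16% |
| 0.7 | 76% | 40% |
| 0.8 | 86% | 54% |
| 1.0 | 97% | 80% |
| 1.3 | >99% | 98% |

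At d=0.7 and 0.004, for example, the noncentrality of 2.711 is below the critical value of 2.998, which gives 40%. Solving for 80% power gives d ≈ 0.74 at 0.05 and d ≈ 1.00 at 0.004.

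**The case against.** The strongest reply is that the sample size does not rest on the pilot contrast. Section 8 opens with a generic detectable difference, between-group d of at least 0.7, which depends on no pilot data, and the pilot effects are offered as support. This stands in part: a generic detectable effect is stated. However, it is stated at 0.05, is not tied to alcohol-minus-placebo change, and is not the threshold that section 4 sets for connectivity. The conclusion about both aims then follows with the pilot data as its only aim-specific evidence.

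Three stronger readings are tempting, and the documents do not support them.

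- **That Aim 2 is underpowered.** No effect size is given for the tested contrast, and the upper pilot values are very large. Absence of a basis is not evidence of a shortfall.
- **That the baseline contrast overstates the placebo contrast by some share.** Expectancy or session effects common to both groups would cancel in the group comparison, and effects could also oppose that of alcohol. Section 3 reports "differences in ventral brain networks when viewing emotional stimuli for the first time compared to the second time", but the pilot's baseline scan is not described, so it is unknown whether this enters the pilot effects. No dilution figure can be derived.
- **That Aim 1 was planned on the wrong population.** A reader might set the outside benchmark (d>1.3) against the inclusion criterion, "diagnosis of bipolar disorder type I". But section 8 already labels that benchmark as "youth at risk for bipolar disorder (defined by previous hypomanic experiences", uses it only as a comparison, and separately gives preliminary Aim 1a effects of 0.7 to 1.3. Section 5 describes a pilot on subjective response as being in bipolar disorder. Nothing shows that the benchmark enters the 3-to-29 range.

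It is also true that no passage says a null Aim 2 result will be read as no difference. That risk is one of interpretation, not something the plan commits to.

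**Conclusion.** The point holds for Aim 2 only, as a statement about what section 8 demonstrates. Its claim of adequate power rests on effects with a different comparator and at a different level from the contrast tested, and the documents contain no estimate for that contrast.

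The size is best expressed as the detectable difference: about one standard deviation of alcohol-minus-placebo change at the connectivity threshold, against the 0.7 that section 8 names at alpha 0.05.

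These figures assume two-sided tests, 30 completers per group, equal variances, and a simple two-sample comparison of change scores for each connection. The mixed model with hemisphere could give somewhat different values. The 0.004 figure applies to the connectivity models. Section 4 gives no threshold for the regional activation part of Aim 2, so the 0.05 figure is shown beside it.

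**What to change.** In section 8:

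1. Remove the alcohol-versus-baseline effects from the Aim 2 justification, and recalculate the 3-to-29 range without them, or confine it to Aim 1.
2. State that no alcohol-versus-placebo effect estimate is available for Aim 2. If the sponsor holds one, report it with its group sizes.
3. Replace the adequacy statement for Aim 2 with a detectable difference, for example:

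> With 30 completers per group and a two-sided test at the connectivity threshold of 0.004, the study has 80% power for a between-group difference in alcohol-minus-placebo change of about d=1.00 (about 0.74 at two-sided 0.05), by a two-sample t approximation. Power at d=0.7 is about 40% (76% at 0.05).

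The sidedness of the test should be stated with it, since the existing figure of over 80% is reproduced one-sided but not two-sided at n=30.

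The cost is wording only. Enrolment, procedures and the analysis model stay as they are. The drawback for the sponsor is that the stated adequacy for Aim 2 becomes less favourable.

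### The pilot-based range of N=3 to N=29 cannot support the claim of adequate power with 30 per group at the smallest healthy-group pilot effect listed (within-subject d=0.4)

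*Combined protocol and SAP*

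**What the plan says.** Section 8 justifies 30 per group in two steps.

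- **Detectable effects.** "At an alpha=0.05, 30 subjects per group will provide >80% statistical power" for a within-subject d of 0.5 or more and a between-group d of 0.7 or more. Sidedness is not given.
- **Pilot data.** Between-group d of 0.7 to 1.3 for subjective response (Aim 1a) and correlations of 0.7 to 0.9 with drinking patterns (Aim 1b). For the healthy group's scans the text reads: "when comparing alcohol scan to baseline scan for Aim 2) with Cohen's d ranging from 0.4 to 3.3". Effects in the bipolar group on the same scan comparison are described as small, down to 0.03.

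The pilot effects are then turned into a sample size: "Calculated sample size required to reach significance from pilot data ranged between $N=3$ to $N=29$ across both aims". The next sentence draws the conclusion: "The recruitment of 30 per group through this application ensures adequate power for testing our hypothesis". The sample sizes are for completers: "30 participants with bipolar disorder and 30 typically developing comparison young adults will complete the study".

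**The concern.** The sentence with the range names a criterion, reaching significance, but no power. The sentence after it makes a claim about power. These are different quantities. If an observed effect just gives p=0.05 at some N, and the true effect equals the observed one, a new study of that size reaches significance about half the time.

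The claim of adequacy is also unqualified, although the Aim 2 pilot range starts at d=0.4, below the within-subject threshold of 0.5 that the same section sets for its >80% statement.

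What is at stake is interpretation. If a within-group change of about that size were missed, the text as written would let the null result be read as coming from an adequately powered study.

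**Working it through.** **Inputs (Section 8).** Alpha 0.05; 30 completers per group; healthy-group within-subject d from 0.4 to 3.3; between-group d from 0.7 to 1.3. Assumptions: d is on the SD-of-differences scale, so a paired t-test applies; sidedness is not stated, so both are shown. The bipolar-group value of 0.03 is left out, because the hypothesis expects little change there.

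**Formulas.**
- Just significant: smallest n with d·√n ≥ t(0.975, n−1).
- Power, paired: P[T′(n−1, d·√n) > t(1−α/s, n−1)], where T′ is noncentral t and s is the number of sides.
- Power, two groups of n: the same with 2n−2 degrees of freedom and noncentrality d·√(n/2).

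**Step 1. The plan's range, read literally (two-sided).**

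| d | n | d·√n | t(0.975, n−1) | p<0.05? |
|---|---|---|---|---|
| 3.3 | 2 | 4.67 | 12.71 | no |
| 3.3 | 3 | 5.72 | 4.30 | yes |
| 0.40 | 26 | 2.040 | 2.060 | no |
| 0.40 | 27 | 2.078 | 2.056 | yes |
| 0.385 | 28 | 2.037 | 2.052 | no |
| 0.385 | 29 | 2.073 | 2.048 | yes |

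Both ends reproduce, since 0.385 prints as 0.4. Power at n=29 and d=0.385 is 51.7% two-sided.

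**Step 2. The range read as an 80% power requirement.**

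| Paired d | N, two-sided | N, one-sided |
|---|---|---|
| 3.3 | 3 | 3 |
| 0.35 | 67 | 52 |
| 0.40 | 52 | 41 |
| 0.449 | 41 | 33 |

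The lower end, 3, fits this reading too, so it does not separate the two. The upper end does not fit: the smallest N for any d that rounds to 0.4 is 33.

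**Step 3. Could 29 come from Aim 1?** Yes. For a between-group test at 80% power, 29 per group is the requirement at d=0.67 one-sided or d=0.749 two-sided, and both print as 0.7. But the range is given for both aims together, so its maximum must also cover the Aim 2 effect of 0.4, which needs at least 33 (Step 2).

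**Step 4. Power with 30 participants, paired.**

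| d | Two-sided | One-sided |
|---|---|---|
| 0.35 | 46% | 59% |
| 0.40 | 56% | 69% |
| 0.449 | 66% | 78% |

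For d=0.40 the noncentrality is 0.40·√30 = 2.19, against critical values of 2.045 (two-sided) and 1.699 (one-sided). Solving the power formula for 80% at n=30 gives d=0.53 two-sided or 0.46 one-sided.

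**Step 5. Which sidedness does the plan use?** At n=30, within-subject d=0.5 has 75.4% power two-sided and 84.8% one-sided. At 30 per group, between-group d=0.7 has 76.0% and 85.0%. The >80% statement therefore fits only one-sided testing at 0.05. The literal reading in Step 1 fits only two-sided: one-sided, the just-significant N is 19 at d=0.40 and 24 at d=0.35, never 29.

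**The case against.** The strongest defence is that the sentence says what it means. It speaks of reaching significance, and on that criterion the range reproduces. A reader might infer that the plan's arithmetic is wrong or that the range contradicts the pilot effects. The documents do not support that. The fault lies in using the range to claim power.

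A reader might also infer that 29 can only be the just-significant N for d of about 0.4. That does not hold either: Step 3 gives an Aim 1 source at 80% power, and the plan does not say which effect produced 29. This removes the unique match but does not rescue the maximum across both aims.

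Three further points stand in part:

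- **Sidedness.** The 52 and 56% assume two-sided testing, while the plan's own >80% figures fit one-sided. Both sets must be shown. The conclusion is the same under each, since the most favourable case is 78%.
- **Stated threshold.** The >80% claim is limited to within-subject d of 0.5 or more, so the plan does not claim 80% at 0.4 there. But the later sentence claims adequacy without that limit, directly after listing 0.4 among the effects relied on. The detectable-effect statement is also a separate argument for 30, so the range is not the only support for the sample size.
- **Relevance to the hypothesis test.** The 0.4 is a healthy-only comparison of alcohol with baseline. Section 4 plans group-by-condition models of alcohol against placebo. This stands in full: 56% must not be read as the power of those models.

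**Conclusion.** The point holds as one about criterion and inference. Either N=3 to N=29 is the N that just reaches p<0.05, which carries about 50% power and cannot show adequacy, or it is an 80% power requirement, and then its maximum is too low for paired d=0.4 (52 two-sided, 41 one-sided, at least 33 under any rounding). With 30 participants, power at d=0.4 is 56% two-sided or 69% one-sided, and 46% to 78% over rounding and sidedness. That is short of 80% in every case.

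This rests on a paired t-test at alpha 0.05, d on the SD-of-differences scale, and 30 completers analysed.

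A reader might go further and infer that the trial as a whole is underpowered, or has a 56% chance of success. These figures do not show that. They concern one pilot contrast in one group, and the section gives no pilot effect for the group-by-condition interaction from which its power could be worked out.

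**What to change.** Reword two sentences in Section 8; enrolment and analysis do not change.

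1. **The range.** State the criterion, the sidedness and the effect behind each end of N=3 to N=29. If it is the N at which the observed effect just gives p<0.05, say so and do not use it as evidence of adequacy. Give the 80% power N for the pilot effects beside it; for paired d these are 3 at 3.3, and 52 (two-sided) or 41 (one-sided) at 0.4.
2. **The conclusion.** Replace the adequacy claim with what 30 participants provide: 80% power for a paired d of about 0.53 two-sided (0.46 one-sided), and 56% (69% one-sided) at d=0.4. Add that these are healthy-group, alcohol-versus-baseline effects and do not give the power of the planned group-by-condition test.

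Use one sidedness throughout the section, including the >80% statement. The cost is a few lines of text and a less favourable stated figure.
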